16.3	Regulatory Authorities.....	23
16.4	Informed Consent	24
16.6	Emergency Contact with Investigators.....	24
16.7	Notification of Primary Care Physician.....	24
16.10	Protocol Amendments	24
16.11	Protocol Compliance	24
16.12	Archives: Retention of Study Records	24
17	References.....	25

ABBREVIATIONS AND DEFINITIONS OF TERMS (examples only – modify as appropriate)

AE	Adverse Event
BMI	Body Mass Index (weight in kg divided by height in m ²)
BO	Bowels Open
CTN	Clinical Trial Notification
ECG	Electrocardiogram
IEC	Independent Ethics Committee
IV	Intravenous
Hr	Hour
MBH	Mackay Base Hospital
NHMRC	National Health and Medical Research Council
PI	Principal Investigator
®	Registered Product
ROP	Ropivacaine
SAE	Serious Adverse Event
SD	Standard Deviation
US	Ultrasound
UTI	Urinary Tract Infection
VAS	Visual analogue scale (Score of 1-10 for pain)
VTE	Venous Thromboembolism

Protocol Number: 1.02 Version 3

Protocol Title: Randomised single blinded trial of surgically placed pre-peritoneal vs ultrasound placed rectus sheath catheters post laparotomy

1 Synopsis

Study Title:

Randomised single blinded trial of surgically placed pre-peritoneal vs ultrasound placed rectus sheath catheters post laparotomy

Protocol Number:

1.02

Indication:

Patient undergoing a laparotomy (Emergency and Elective) under the general surgical team

Study Drugs:

Testing technique, not drugs. Both arms will then receive 20mL 0.2% Ropivacaine infusion through these catheters every 4 hrs for 3 days.

No. Participants:

72 Patients

No. Centres:

1 Centre; Mackay Base Hospital

Study Duration:

Approximately 1 year

Objectives of the Study:

The goal of this project is to prove if surgically placed pre-peritoneal catheters are more effective than ultrasound placed rectus sheath catheters at improving post-operative pain.

Study Endpoints:

The primary endpoint is:

- Total narcotic usage until day 3 post op. This will be measured in mg of IV Morphine. All other narcotic agents (Oral or IV) will be calculated back to IV Morphine equivalence as per dosage equivalence on MIMs.

Secondary endpoints:

- Time taken for procedure (Minutes)
- Patient blinded VAS scores at rest and coughing (0-10)
- Time till flatus (Days)
- Time till BO (Days)
- Time till discharge (Days)
- Complications
 - o Wound infection
 - o UTI
 - o VTE

Study Design:

All enrolled patient will be randomised into two even arms via random allocation sequence in numbered envelopes. A third party doctor using computer randomisation will conduct the randomisation prior to commencement of the project. The allocation will be revealed prior to closure of the abdomen where the patient will either receive a surgically placed pre-peritoneal catheter or an ultrasound guided rectus sheath catheter inserted by the anaesthetic team prior to waking up from the general anaesthetic.

These catheters will then be intermittently infused with local anaesthetic over the next 72 hours via a pump. Over this time the patients' opiate analgesic requirement and the visual analogue scale (VAS) will be monitored daily. The surgical team and the anaesthetic pain team will review the patients daily for the above and monitor for adverse effects from the procedure/local anaesthetic.

Eligibility Criteria (Inclusion and Exclusion)

Inclusion: All adult general surgical patients undergoing a midline laparotomy at Mackay base hospital

Exclusion Criteria:

- Local Anaesthetic allergy
- Catheter plastic allergy
- Multiple operations as defined as alteration of anatomy of the abdominal wall, preventing placement of catheters.
- Chronic abdominal pain as defined as abdominal pain with opiate use for > 12 weeks
- Abdomen left open
- Patient under 18 years of age
- Pregnant
- Inability of surgical/anaesthetic staff to perform procedure
- Patients with altered cognition (dementia or delirium) and therefore unable to respond to

VAS.

- Patients intubated & therefore unable to communicate

Sample Size Determination:

Calculation of the sample size was performed by using the primary endpoint of 72-hour total morphine usage post laparotomy. In a similar previous study, the total dose of administered morphine was 62mg with a standard deviation of 16mg.⁴ It was decided that a difference of 20% (12mg) would be considered clinically relevant, similar to this previous study.

Assuming $\alpha = 0.05$ and $\beta = 0.15$ (a power of 85 per cent), a total of 66 patients (33 patients per group) would be required to find there was no difference between each group¹⁰. Assuming a 10% dropout rate 72 patients need to be recruited (36 patients per group) to make this number.

2 Introduction

Adequate postoperative analgesia post midline laparotomy has been associated with a decrease in cardiopulmonary complications, mortality, length of hospital stay and therefore a decrease in hospital costs.¹⁻²

Opiate analgesic requirements post laparotomy are usually quite high and can have significant side effects such as respiratory depression, nausea, ileus, confusion and urinary retention.² To minimise opiate usage and therefore side effects a multimodal approach to pain with adjuvants such as Epidural or rectus sheath catheters are often used.³

Epidural analgesia, whilst being shown to be more effective than rectus sheath catheters in reducing post operative pain in most publications have numerous shortfalls.² They often don't have time to be placed in emergency laparotomies, have multiple contraindications and have rare, but clinically significant complications such as an epidural abscess or haematoma. They also require more monitoring post operatively and associated with significantly higher rates of hypotension post operatively.²

Whilst most studies have demonstrated efficacy of rectus sheath catheters, some older studies found no benefit compared with placebo. A recent systematic review and meta-analysis have shown that it does significantly decrease total opioid consumption.⁵ Moreover, recent studies looking at more secondary endpoints have demonstrated a decreased time to recovery of bowel function, earlier mobilisation and decreased hospital stay when using rectus sheath catheters.^{5,6,7}

Potentially the heterogeneity in the data in regards to of rectus sheath catheters in large is due to a wide variety of techniques used in their placement.⁴

In regards to safety of the rectus sheath catheters with continuous LA infusion, no studies have reported any significant complications.⁵ Two small studies have been done looking for specific complications. The first was an observational, descriptive and prospective study of 50 patients which found that there was no increased incidence of wound infection with a rectus sheath catheter than without post laparotomy.⁹ The second study looked at blood levels, signs or symptoms of LA toxicity in 12 patients who had an U/S guided rectus sheath catheter placed.⁸ The protocol of LA used involved a 20mL bolus of 0.5% ROP followed by 10 mL/h of 0.2% ROP infusion. It found that although the total plasma ROP concentrations just exceeded reported neurotoxicity thresholds, the unbound ROP concentration did not reach the toxicity threshold, and nil patients had any signs or symptoms of toxicity.⁹

It is standard practice for the placement of rectus sheath catheters following major abdominal surgery. A surgeon will insert the rectus sheath catheters prior to closure of the laparotomy incision abutting the transversalis fascia in the pre-peritoneal space. Alternatively an anaesthetist will insert the rectus catheters via US guidance into the rectus abdomini muscle. A detailed description of the technique used by both surgeons and anaesthetist in this study is included in section 7.4 of this protocol. Whilst in the literature both techniques of surgically placed pre-peritoneal catheters and US placed rectus sheath catheters have been found to be effective against placebo there have been no head to head trials to see if one is superior.

The only study directly comparing catheter placement was Khorgami et al.⁴ They compared catheter placement in the rectus sheath (intrafascial) to the Subcutaneous (suprafascial) space. In this study it found that the intrafascial rectus sheath catheters were more effective in reducing morphine requirements, visual analogue scale (VAS) scores and time til BS returns than suprafascial catheters.

This study will be similar in nature to the aforementioned study⁴ with the intention of finding whether a surgically placed pre-peritoneal catheter is a quicker, more effective option to the U/S placed

intrafascial rectus catheter. The other potential benefit theorised would be a decrease in visceral pain with a pre peritoneal catheter.

In this study, the catheters will be inserted and secured by either a surgical or anaesthetic consultant. Surgical consultants and anaesthetic consultants will be orientated to the standard specified procedure (as detailed in section 7.4 of this protocol) of placement as led by [name] (Director of Surgery) prior to the commencement of this study.

3 Objectives

Null hypothesis: Surgically placed pre-peritoneal catheters are superior to ultrasound placed rectus sheath catheters at reducing post-operative pain.

The primary endpoint is:

- Total narcotic usage until day three post op. This will be measured in mg of IV Morphine. All other narcotic agents (Oral or IV) will be calculated back to IV Morphine equivalence as per dosage equivalence on MIMs.

Secondary endpoints:

- Time taken for procedure (Minutes)
- Patient blinded VAS scores at rest and coughing (0-10)
- Time till flatus (Days)
- Time till BO (Days)
- Time till discharge (Days)
- Complications
 - o Wound infection
 - o UTI
 - o VTE

4 Study Design

This will be a randomised, patient blinded trial. All enrolled patient will be randomised into 2 even arms – One to receive a surgically placed pre-peritoneal catheter, the other an ultrasound guided rectus sheath catheter inserted by the anaesthetic team prior to waking up from the general anaesthetic. Both will then receive 72 hours of intermittent Ropivacaine 0.2% boluses via these catheters.

Patients will be screened for the study when they are booked up for an emergency or elective procedure which will always or potentially require a midline laparotomy. These patients will then be consented for potential enrolment. Enrolment and allocation will be only revealed when it is sure that the patient does not meet any of the exclusion criteria in theatre prior to closure of the abdomen via randomised numbered envelopes.

These numbered envelopes will be generated prior to the start of the study by a 3rd party doctor. This doctor, who is not involved in the study in any other way, will use a random allocation sequence generated by computer using non-blocking randomisation.

Over the first 72hours the patients' opiate analgesic requirement, the visual analogue scale (VAS) and potential complications will be monitored daily by the surgical team and recorded on the data collection tool. During this time the anaesthetic team will also review the patient to monitor the local anaesthetic boluses are being administered correctly via the pumps and to look for adverse effects from the

procedure/local anaesthetic as well. After the 72 hours, unless to patient has ongoing pain issues, the surgical team alone will continue to see the patient daily and record any delayed complications until discharge.

This follow up, other than recording on the data collection sheet, is currently routine care for patients post laparotomy with rectus sheath catheters and will not significantly increase workload for the teams involved during the trial period.

5 Study Population

5.1 Number of participants

72 patients (36 patients per arm)

The following demographics and primary clinical characteristics which may cause a difference between the arms are outlined below. These will be record and analysed between the 2 arms to ensure there is nil significant bias.

Demographic factors

- Sex
- Age
- BMI
- ASA Score
- Creatnine

Primary clinical characteristics

- Procedure
- Procedure time
- Incision type (Full midline, upper midline, lower midline)
- Incision Length
- Stoma
- HDU/ICU Requirement
- Anaesthetic used

5.2 Inclusion Criteria

All adult general surgical patients undergoing a midline laparotomy

5.3 Exclusion Criteria

- Local Anaesthetic allergy
- Catheter plastic allergy
- Multiple operations as defined as alteration of anatomy of the abdominal wall, preventing placement of catheters.
- Chronic abdominal pain as defined as abdominal pain with opiate use lasting > 12 weeks
- Abdomen left open
- Patient under 18
- Pregnant
- Inability of surgical/anaesthetic staff to perform procedure
- Patients with altered cognition (dementia or delirium) and therefore unable to respond to VAS.
- Patients intubated & therefore unable to communicate

6 Study Assessments and Procedures

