7.5 Randomisation Procedure

Randomisation will occur via a random allocation sequence which will be made by a third party ([name]) via computer randomisation prior to the project. There will be no restrictions such as blocking on this randomisation. The concealed sequence will be in ordered closed envelopes and only once the patient is enrolled will the arm they are allocated be revealed.

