10.2 Sample Size

Calculation of the sample size was performed with looking at the primary endpoint of total morphine usage post laparotomy. In a similar previous study the total dose of administered morphine was 62mg with a standard deviation of 16mg.⁴ As stated above it was decided that a difference of 20% (12mg) would be considered clinically relevant, similar to this previous study.

A: Assuming $\alpha = 0.05$ and $\beta = 0.15$ (a power of 85 per cent), a total of 62 patients (31 patients per group) would be required to find there was no difference between each group.¹⁰

This means that with this sample size this study has an 85% chance of finding out if there is a statistically significant ($p < 0.05$) 20% reduction in total narcotic usage until day 3 post op with surgically placed, instead of U/S guided rectus sheath catheters.

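### Patients on regular opioids for non-abdominal pain, or for 12 weeks or less, are eligible; their habitual dose counts in the primary endpoint and is not a listed baseline factor

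*Protocol*

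**What the plan says.** Section 5.2 includes "All adult general surgical patients undergoing a midline laparotomy". Among the exclusions in section 5.3, one refers to opioid use: "Chronic abdominal pain as defined as abdominal pain with opiate use lasting > 12 weeks". The synopsis has nearly the same line: "Chronic abdominal pain as defined as abdominal pain with opiate use for > 12 weeks". Both tie the exclusion to abdominal pain and to a duration above 12 weeks.

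Section 3 defines the primary endpoint as "Total narcotic usage until day three post op. This will be measured in mg of IV Morphine", and adds that "All other narcotic agents (Oral or IV) will be calculated back to IV Morphine equivalence as per dosage equivalence on MIMs". No rule separates a dose the patient was already taking from opioid given for the laparotomy.

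Section 5.1 introduces its baseline list with "The following demographics and primary clinical characteristics which may cause a difference between the arms are outlined below". The list holds sex, age, BMI, ASA score, creatinine and items on the procedure, incision, stoma, HDU/ICU need and anaesthetic. Pre-operative opioid use is absent there and from the assessment table in section 6.2.

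Section 7.5 states that "There will be no restrictions such as blocking on this randomisation". Section 10.2 plans on a cited trial in which "the total dose of administered morphine was 62mg with a standard deviation of 16mg", with a difference of 12 mg taken as clinically relevant.

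**The concern.** The criterion depends on where the pain is and how long it has been treated. The endpoint depends on how much opioid the patient takes, for whatever reason. The two do not match. A patient on long-term opioids for back pain or arthritis, on opioid substitution, or with 11 weeks of opioids for abdominal cancer pain passes section 5.3. If the habitual dose continues after surgery, all of it enters the 72-hour total, although catheter position has no bearing on it.

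This is the only endpoint on which the trial is powered. Spread from habitual dosing makes a real difference harder to detect. With about 36 patients per arm and unrestricted allocation, such patients can also fall unevenly by chance, and the section 5.1 comparison of the arms would not show it.

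**Working it through.** **Reproducing the plan.** Inputs from the synopsis and section 10.2: difference 12 mg, SD 16 mg, alpha 0.05, power 85%. Sidedness is not stated; two-sided is assumed because a one-sided calculation gives 52 in total and does not match. The standardised difference is 12/16 = 0.75. A two-sided t-test then needs 32.9, so 33 per group and 66 in total, which is the synopsis figure. Power with 33 per group is 0.851. (Section 10.2 gives 62 instead of 66; that is a separate matter.)

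**Assumptions for the check.** The documents give neither input below, so ranges are used.
- p, the share of enrolled patients on a habitual opioid: 3%, 5%, 10%.
- e, the IV morphine equivalent this adds over 72 hours: 30, 60, 100 mg. At an assumed 3:1 oral-to-IV ratio, 60 mg oral morphine a day gives 60/3 × 3 days = 60 mg.
- All other patients have SD 16 mg, and the habitual dose is fully continued.

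**Formula.** SD' = √(16² + p(1−p)e²).
- Lowest case: √(256 + 0.03 × 0.97 × 900) = √282.2 = 16.8 mg.
- Highest case: √(256 + 0.10 × 0.90 × 10,000) = √1156 = 34.0 mg.

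**Power.** Simulated, 33 per group, true difference 12 mg, two-sided 5% level:

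| p | e (mg) | SD' (mg) | t-test | Mann-Whitney |
|---|---|---|---|---|
| 0 | – | 16.0 | 0.85 | 0.83 |
| 3% | 30 | 16.8 | 0.82 | 0.80 |
| 3% | 60 | 19.0 | 0.72 | 0.78 |
| 3% | 100 | 23.4 | 0.56 | 0.78 |
| 5% | 30 | 17.3 | 0.79 | 0.79 |
| 5% | 60 | 20.7 | 0.65 | 0.75 |
| 5% | 100 | 27.0 | 0.46 | 0.75 |
| 10% | 30 | 18.4 | 0.74 | 0.74 |
| 10% | 60 | 24.1 | 0.52 | 0.66 |
| 10% | 100 | 34.0 | 0.30 | 0.65 |

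**Chance imbalance.** One extra such patient in an arm of 36 moves its mean by e/36: 30/36 = 0.8 mg, 60/36 = 1.7 mg, 100/36 = 2.8 mg. To reach 12 mg by imbalance alone takes 12 × 36/100 = 4.3, so an excess of 5 at 100 mg, or 12 × 36/60 = 7.2, so 8 at 60 mg. The expected number of such patients among all 72 is 2.2, 3.6 and 7.2 at the three shares. In simulation with 36 per arm, an excess of 5 or more in either arm occurs in 0.3%, 1.6% and 7.6% of trials; an excess of 8 or more occurs in under 0.4% throughout. This imbalance is the same variance that the power figures already count, not a second loss.

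**The case against.** Broad eligibility is a legitimate choice when two routine techniques are compared, and any cut-off has patients just outside it. This stands, and it is why widening the exclusion is only an option here.

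The size of the effect rests on assumed shares and doses, and the mild cases lose little. This also stands. A rank test is much less sensitive to a few very high totals. Section 10.3 presents morphine use as normally distributed but fixes no test for it and leaves other testing to the statistician. Choice of test and adjustment may also sit in a SAP that is not at hand. The table therefore shows both tests. Even so, adjustment needs a baseline value, and section 5.1 does not list one.

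A reader might infer three stronger things that the documents do not support.
- That a few opioid-tolerant patients could outweigh the 12 mg target. That takes an excess of 5 to 8 in one arm at 60-100 mg, which is rare on the shares assumed.
- That the planning SD leaves no room for such patients. The cited trial's eligibility is not in the documents, so its SD of 16 mg may already include some.
- That the habitual dose could never be subtracted or adjusted for. The data collection tool is not shown, and section 6.2.2 lets investigators work out opioid doses retrospectively from charts.

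Nor does the text show that such patients will be enrolled, only that they are eligible.

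**Conclusion.** The point holds in a limited form. Regular opioid users outside the abdominal-pain, over-12-weeks definition are eligible, any continued habitual dose counts in the primary endpoint, and pre-operative opioid use is not a listed baseline factor. Randomisation keeps the comparison free of systematic bias, so the cost is precision and chance imbalance. With 33 per group, t-test power falls from 85% to somewhere between 82% and 30%, or to between 80% and 65% with a rank test.

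Those ranges depend on 3-10% users, an added 30-100 mg, full continuation of the habitual dose, and an SD of 16 mg that does not already include such patients. The worst figure needs both the highest share and the highest dose. This is a cheap improvement in precision, not a flaw that invalidates the design.

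**What to change.** Add the regular pre-operative daily opioid dose to the section 5.1 characteristics and to the data collection tool. Express it in IV morphine equivalent with the same conversion source as the endpoint, take it from the medication history, and enter zero for non-users. Capture it before the de-identification and disposal of collection forms described in section 11. State in section 10.3 that the primary comparison is adjusted for this dose. To the extent that the habitual dose is accurately recorded and continued, adjustment brings the residual SD back towards 16 mg.

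The cost is one field and an adjusted instead of an unadjusted primary analysis. Eligibility and recruitment do not change.

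As an option, the sponsor may instead key the exclusion in section 5.3 and the synopsis to regular pre-operative opioid use for any indication, with a look-back period of its choosing and a statement on opioids given only for the acute presenting illness. That loses some screened patients, and the result would then not apply to regular opioid users.

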7.4 Techniques

Technique for Anaesthetically inserted rectus sheath catheter

- 1) The procedure takes place after abdominal wall closure, prior to dressings.
- 2) From the superior aspect of the incision a point 5-7cm lateral and 3cm cranial OR at the costal margin (If this former point is superior to the costal margin) is marked for the catheter insertion.
- 3) Under U/S guidance at this marking a 16G Tuohy Needle is inserted at approximately 30-45 Degrees in either a lateral to medial direction (To avoid epigastric arteries) or caudal direction or a combination.
- 4) When the tip of the needle is just below the rectus muscle before going through the posterior rectus sheath (Intrafascular space) some of the 20mL of 0.2% Ropivacaine is infused to hydro dissect and open up the space. See figure 2 for the correct placement
- 5) The angle of insertion is then dropped to parallel with the skin and the needle is advanced further.
- 6) The 16G Epidural Catheter is then inserted through the needle to approx. 10-15cm and the needle is withdrawn slowly to ensure the catheter does not move.
- 7) The Catheter is then secured with the Securement Device.
- 8) The catheter connector, followed by the filter is then attached to the distal end of the catheter
- 9) The process is then repeated on the contralateral side.
- 10) The remainder of the 20mL of 0.2% Ropivacaine is infused on each side.

[figure not shown]
Figure 2: U/S placement location (Intrafascicular)

Technique for Surgically inserted rectus sheath catheter

- 1) The procedure takes place just prior to abdominal wall closure.
- 2) From the superior aspect of the incision a point 5cm lateral and 3cm cranial OR at the costal margin (If this former point is superior to the costal margin) is marked for the catheter insertion.
- 3) At this marking a 16G Tuohy Needle is inserted at approximately 45 Degrees in a caudal direction, parallel to the incision.
- 4) With the surgeon's other hand the inside the abdominal cavity, deep to the site of insertion, the needle is advanced until it has just passed through the rectus sheath and just lies in the pre-peritoneal plane.
- 5) The angle of insertion is then dropped to parallel with the skin and the needle is advanced further with the surgeon's other hand used to palpate the needle and ensure it remains in the correct plane.

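### Three exclusion criteria carry no time point and can become true after the envelope is opened, and nothing keeps those patients in their arm; failed placement is the main risk of bias

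*Protocol*

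**What the plan says.** Section 5.3 lists three exclusions without a time point: "Inability of surgical/anaesthetic staff to perform procedure", "Patients with altered cognition (dementia or delirium) and therefore unable to respond to VAS", and "Patients intubated & therefore unable to communicate". The synopsis repeats the list.

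Section 4 ties eligibility to the reveal: "Enrolment and allocation will be only revealed when it is sure that the patient does not meet any of the exclusion criteria in theatre", before the abdomen is closed. The synopsis agrees ("The allocation will be revealed prior to closure of the abdomen"), and section 7.5 adds that "only once the patient is enrolled will the arm they are allocated be revealed".

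Section 7.4 sets the insertion times. For the surgical catheter, "The procedure takes place just prior to abdominal wall closure". For the ultrasound catheter, "The procedure takes place after abdominal wall closure, prior to dressings".

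Three other places bear on what happens afterwards. Section 9.1 defines completion as catheters placed plus 72 hours of boluses. Section 9.2 lists catheter or wound infection, any SAE and patient request as grounds for discontinuation. Section 10.3 allows a patient with missing information to be left out of the analysis, with the reason reported.

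**The concern.** An exclusion that can be met after allocation gives staff a ground for removing a randomised patient. Section 4 is meant to prevent this, but for some of the listed events the certainty it asks for cannot be had at the time of the reveal.

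Failed placement is the most serious case because the protocol's own procedures tie it to the arm. A surgeon places one catheter by palpation through the open abdomen, and an anaesthetist places the other under ultrasound after closure. Only the patient is blinded, so whoever decides that the procedure could not be performed knows the allocation. If those patients leave the comparison and tend to need more opioid, the trial compares successful placements, and the technique that fails more often looks better than it is.

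**Working it through.** **Timing of each criterion against the reveal**

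| Criterion (5.3) | Can be known before the envelope | Can become true only later |
|---|---|---|
| Staff unable to perform the procedure | Staff not available or not trained; placement judged not feasible | An attempt that fails: both insertions follow the reveal, and the ultrasound one also follows closure |
| Intubated, unable to communicate | Already ventilated before surgery; post-operative ventilation planned | Unplanned continued ventilation. The patient is under general anaesthesia at the reveal, so this cannot be ruled out then |
| Altered cognition | Dementia; pre-operative delirium | Post-operative delirium. The first VAS is 12 hours after surgery (6.2.2) |

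Each criterion therefore has one part that section 4 can handle and one part that it cannot.

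**Size of the possible bias.** The plan gives no figure for this, nor any rate of failed placement, ventilation or delirium. From the documents come the 12 mg target difference, the SD of 16 mg and 36 patients per arm. As a check on these inputs, a two-sided two-sample t-test at α = 0.05 and 85% power with 12 mg and 16 mg gives 32.9, so 33 per group, which is the synopsis figure of 66.

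Assumed: a share p of one arm is removed, and those patients use d mg more than the patients who remain. The full-arm mean equals the remaining patients' mean plus p × d, so removal lowers the arm mean by p × d.

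| p | d (mg) | Shift p × d (mg) | Shift / 12 mg |
|---|---|---|---|
| 5% | 8 (0.5 SD) | 0.4 | 3% |
| 10% | 16 (1 SD) | 1.6 | 13% |
| 15% | 16 (1 SD) | 2.4 | 20% |
| 15% | 24 (1.5 SD) | 3.6 | 30% |

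With removals in both arms the net bias is p₁d₁ − p₂d₂. It is zero when the two products are equal. With 10% against 5%, both at 16 mg, it is 1.6 − 0.8 = 0.8 mg. It is also zero if the removed patients use no more opioid than the rest (d = 0).

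**Effect on false-positive error** (normal approximation, no true difference). The standard error is 16 × √(1/36 + 1/(36(1 − p))). At p = 0.15 this is 3.93 mg.
- p = 5%, d = 8 mg: two-sided error about 5.1%.
- p = 15%, d = 16 mg: 2.4/3.93 = 0.61 standard errors, about 9.4%.
- p = 15%, d = 24 mg: 3.6/3.93 = 0.92 standard errors, about 15%.

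**Effect on power.** Removing 15% of 36 is about 5 patients. Power for 12 mg (normal approximation) goes from 88.9% with 36 against 36 to 86.5% with 36 against 31. The loss is small, so the issue is bias.

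**The case against.** The strongest reply is that the protocol already places eligibility before allocation. Section 6.1 applies exclusions at screening, section 4 checks again in theatre, and section 7.5 reveals the arm only after enrolment. Dementia, pre-operative delirium, staff availability and planned ventilation can all be known by then. A reader might infer that the three criteria can be known only after the envelope is opened. That goes too far, and the objection stands against it.

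A reader might also infer that the protocol requires removal after randomisation. It does not. Section 9.2 names none of these events as such, section 9.1 defines completion and not an analysis set, and failed placement does not by itself make charted opioid data missing. Section 5.1 lists HDU/ICU requirement among the characteristics to compare between arms, which suggests that sicker patients are expected to stay in. This stands too: removal is permitted by silence, not ordered.

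Thirdly, the wording on staff inability may refer to availability or skill and not to a failed attempt, since abdominal wall anatomy that prevents placement has its own criterion. The text supports either reading. That ambiguity is part of the fault, because nothing else in the protocol says what happens after a failed attempt.

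A further reply is that analysis sets are commonly left to the statistical analysis plan, which is not shown. That is fair for the definition of sets, and their absence is not the point here. When eligibility is judged belongs to the protocol, and an analysis plan cannot make the list in 5.3 compatible with section 4.

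Finally, keeping every patient has a cost. The endpoint counts all narcotics. If a ventilated patient received opioid sedation totalling 300 mg (assumed), that one patient among 36 would move an arm mean by (300 − 62)/36 = 6.6 mg, over half the 12 mg target. The fix has to allow for this.

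**Conclusion.** The point holds as a fault in the timing of eligibility. Parts of three criteria cannot be settled before the reveal as section 4 requires, and no passage keeps a patient who meets one later in the allocated arm.

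A bias linked to arm is supported by the protocol's own procedures only for failed placement. It would be tempting to say that all three criteria remove patients differently by arm, but nothing in the documents links continued intubation or delirium to catheter technique; for those a difference is possible and not shown.

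The range of 0.4–3.6 mg (3–30% of the target) rests on assumed removal of 5–15% in one arm only and an assumed 8–24 mg excess. It shows what could happen, not what is expected, and which arm would be favoured is unknown. The change should be made, because it is cheap and the bias could not be reliably undone if patients were dropped and their data not kept.

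**What to change.** Reword 5.3, with the matching synopsis list, and section 4 so that each criterion is judged on what is known before the envelope is opened:
- both teams are available and judge placement feasible;
- no post-operative ventilation is planned;
- no dementia or pre-operative delirium is present.

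State in section 4 and 10.3 that once the envelope is opened the patient stays in the allocated arm for the primary opioid analysis, whatever follows with placement, ventilation or cognition. Report failed placement, ventilation and delirium by arm.

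The cost is wording. Section 6.2.2 already allows opioid use to be taken retrospectively from the medication chart, so the primary endpoint needs no response from the patient; VAS scores may still be missing for patients who cannot communicate. The downside is that a few retained patients, above all any ventilated patient given opioid sedation, may make the totals noticeably more variable. A sensitivity analysis without ventilated patients can be reported alongside the primary result.
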